1. PROTOCOL SUMMARY

Title (Acronym)	In teractions between the di et and g ut microbes, metabolism and body composition in preterm infants (INDIGO)
Study centres	Newcastle Royal Infirmary and Chelsea and Westminster NHS Foundation Trust (Imperial College London). Additional sites may be added
Study objectives	To evaluate whether an exclusive human milk diet compared with exposure to cow's milk-based products results in differences in a) gut bacteria (types and diversity, b) stool and urine metabolites and c) body composition
Study design	Randomised open label, controlled trial
Study population	 Inclusion criteria Preterm infants born below 30 completed weeks of gestation (≤ 29 weeks and 6 days) <72 hours age Written informed consent from parents Exclusion criteria Major congenital or life-threatening abnormalities Inability to randomise within 48 hours of birth Exposure to bovine milk product prior to randomisation Likelihood of transfer to another hospital before 34 weeks postmenstrual age
Interventions	• Exclusive human diet (human donor milk and human milk-based fortifier: 'Prolacta RTF 26' and 'Prolacta 6')
Route of administration	Enteral
Target number of patients	At least 100 patients to provide ~80 evaluable infants in total with stool samples for microbiome analysis at 34w PMA
Randomisation	 Using minimisation incorporating the following variables: hospital site, gestation (<25 weeks: ≤24 weeks and 6 days), and multiple birth status Secured, password protected web-based randomisation using minimisation algorithm (www.sealedenvelope.com or similar)
Primary outcomes	 Microbiota: gut bacterial diversity, proportions of specific taxa, e.g. Bifidobacteria species Body composition; adipose tissue mass and non-adipose tissue mass assessed using whole body magnetic resonance imaging (MRI) at term (37-42 weeks postmenstrual age)
Secondary outcomes	Metabolome: Gut derived metabolites and markers of gut function; metabolites include stool Volatile Organic Compounds (VOC, using Gas Chromatography MS), and urine (e.g. using 1H NMR and/or Liquid Chromatography MS); markers of gut health may include those measured in the stool (e.g. calprotectin) and urine (e.g. intestinal fatty acid binding protein, iFABP) Feed and nutrition related outcomes Healthcare resource use Neonatal morbidities and clinical outcomes Adipose tissue volume and distribution
Duration of trial intervention	To 34 weeks postmenstrual age

Duration of study	 Recruitment period: 21 months Total trial duration: 24 months
End of Trial	 37 – 42 weeks at Imperial College. Discharge from neonatal unit at Newcastle
Safety assessments	 Routine assessments until discharge from Neonatal Unit Safety tracking during hospitalisation

258	
259	3. ABBREVIATIONS
260	
261	MOM: Mother's own milk
262	NEC: Necrotising enterocolitis
263	DBM: Donor breast milk
264	MRI: Magnetic Resonance Imaging
265	BAPM: British Association of Perinatal Medicine
266	NNRD: National Neonatal Research Database
267	GCP: Good Clinical Practice
268	HTA: Human Tissue Authority
269	REC: Research Ethics Committee
270	SAE: Serious Adverse Event
271	SOP: Standard Operating Procedures
272	TMG: Trial Management Group
273	SSC: Study Steering Committee
274	DMEC: Data Monitoring and Ethics Committee
275	VOC: Volatile Organic Compounds
276	iFABP: intestinal Fatty Acid Binding Protein
277	MS: Mass Spectroscopy
278	NMR: Nuclear Magnetic Resonance
279	GC: Gas Chromatography
280	LS: Liquid Chromatography
281	PAA: Plasma amino acid
282	SCFA: Short Chain Fatty Acids
283	AT: Adipose Tissue
284	PMA: Postmenstrual age
285	
286	
287	
288	

292

293

294

295

296

297

298

299

300

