8. TRIAL ENDPOINTS

- The outcomes assessed in infants recruited at both sites will be microbiota and metabolomics.
- 438 Infants recruited at Chelsea and Westminster NHS Foundation Trust will be additionally be
- 439 assessed for body composition. Infants recruited in Newcastle will have additional blood
- samples collected and stored for future studies.

441

420

421

422

423

424

425

426

427

428

429

430

431

432

433

434 435

436

- 442 8.1. Primary endpoints
- 8.1.1. Newcastle and Chelsea and Westminster NHS Foundation Trust Hospitals
- 444 8.1.1.1. Stool gut microbiota: Next Generation Sequencing using MiSeq
- 445 8.1.2. Chelsea and Westminster NHS Foundation Trust (Imperial College London)
- 8.1.2.1. Body composition at term equivalent age assessed with whole body Magnetic
- Resonance Imaging (MRI) at 37-42 weeks postmenstrual age
- 448 **8.1.3.** Newcastle
- 8.1.3.1. Salvaged blood for growth factors e.g. IGF-1
- 450 8.1.3.2. Targeted blood: plasma amino acid (PAA) profiles and lymphocyte subsets.

- 452 8.2. Secondary endpoints
- 453 8.2.1.1. Stool metabolomic profile using GC-MS for VOCs
- 454 8.2.1.2. Urine metabolomic profile using LC-MS or NMR
- 455 8.2.1.3. Markers of gut health e.g. urinary intestinal fatty acid binding protein (iFABP)
- and stool calprotectin, using standard biochemical techniques
- 8.2.2. Feeding related outcomes: total number of days on which feeds were withheld on any
- 458 occasion after trial enrolment determined by days of parenteral nutrition (PN); age when
- 459 enteral feeds ≥150ml/kg/day maintained for at least 3 days (coded as age at last PN); total
- days exposed to MOM prior to 34 weeks; feeding mode at discharge (breast, formula or
- 461 mixed)
- 462 8.2.3. Healthcare resource use: total length of stay (days); postmenstrual age at discharge;
- 463 days in intensive, high-dependency and low-dependency care according to national
- 464 definitions (BAPM)
- 8.2.4. Neonatal morbidities and clinical outcomes: survival to discharge; Retinopathy of
- 466 Prematurity requiring intervention; Necrotising Enterocolitis requiring surgery or leading to
- death; blood-culture positive sepsis; total days when any antibiotic administered; chronic
- 468 lung disease (oxygen requirement or need for any pressure support at 36 weeks postmenstrual
- age), peri-ventricular haemorrhage (PVH) and/or presence of parenchymal damage. These

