- Using 16S rRNA bacterial profiling data we will conduct alpha and beta diversity analysis. Based on previously published data by our group[12,13] a Shannon Diversity Index alpha diversity of <1 is representative of infants in the initial weeks of life where the microbiome is undeveloped; a Shannon Diversity Index of >1.5 is representative of infants immediately prior to neonatal unit discharge where the gut microbiome is more developed and risk of gut microbiome mediated disease is significantly reduced. Based on these findings a sample size of 24 in each group (48 in total) is required to achieve over 95% power detect a 0.5SD difference in diversity index. By processing 40 samples in each group we will reach this power for true significance of alpha diversity analysis and note from previous analysis that that this number is also sufficient for beta diversity analyses, including but not limited to UniFrac distance, clustering (PAM and DMM), correlation (CCLasso), ordination analysis (PCA and PCoA), and determining significant differences between the relative abundance of different genera.
- 746 13.1.2 Body composition

Supplementary materials Effect of an exclusive human milk diet on the gut microbiome in preterm infants; a randomised clinical trial

We will compare proportions of key taxa e.g. proteobacteria, firmicutes etc., as well as

numbers and presence of key species including lactobacilli, bifidobacteria and staphylococci.

- In our most recent work in preterm infants born at <31 weeks gestational age, the mean (SD)
- of non-adipose tissue mass was 2.41 (0.46) kg (Uthaya et al. 2016)[14]. A sample size of 20
- 549 babies per group will have 80% power at the 5% significance level (2-sided) to detect a 0.42
- 750 kg between-group difference in non-adipose tissue mass assessed by whole body Magnetic
- 751 Resonance Imaging using protocols previously described[15,14].

752 13.1.3 Metabolome

- 753 Stool VOC analysis identifies several individual compounds; our collaborators show an
- average 31.3±10.5 (Mean and SD) VOCs were identified per sample [16]. With n=40 infants
- per group we will have 85% power to detect an increase in 5 VOCs between intervention and
- standard groups. Urinary 1H NMR studies are limited in preterm infants. However, highly
- 757 significant differences in spectra (p<0.005) were detected between adults born preterm
- 758 (n=19) and term (n=17). The differences observed were in key metabolites such as

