13.2 Analysis plan

13.2.1 Microbiome

The microbial data may be over-parameterised depending on the taxonomic level at which analysis is carried out. At a strain level we will have more microbial strains present in samples than there will be samples taken. However, due to current limitations in sequence read length we have shown that at an Operation Taxonomy Unit (OTU) level (that is sequences with >97% similarity which corresponds to species level), we identify considerably less OTU (138) after normalisation than samples forecast for the proposed study[19]. We will use multivariate ordination techniques to summarise the major trends in variation in bacterial community composition of infant stool and will allow us to identify those taxa most closely associated with changes in the pattern of bacteria over time. We will then use canonical ordination to quantify the impacts of the diet on the microbiome composition.

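### The microbiome primary endpoint is stated differently in four sections of the protocol, and none says which contrast decides

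*Protocol*

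**What the plan says.** Four places in the protocol bear on the microbiome primary.

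- **Section 1, Primary outcomes:** "Microbiota: gut bacterial diversity, proportions of specific taxa, e.g. Bifidobacteria species". The target-number row adds "At least 100 patients to provide ~80 evaluable infants in total with stool samples for microbiome analysis at 34w PMA".
- **Section 8.1.1.1, Primary endpoints:** "Stool gut microbiota: Next Generation Sequencing using MiSeq". This is a laboratory method, without a variable, summary measure or time point.
- **Section 13.1.1, Gut bacteria (sample size):** alpha and beta diversity analyses are announced and the Shannon index is discussed. The sample size is then "of 24 in each group (48 in total) is required to achieve over 95% power detect a 0.5SD difference in diversity index", followed by "By processing 40 samples in each group we will reach this power for true significance of alpha diversity analysis". The same number is said to suffice for beta-diversity work, "including but not limited to UniFrac distance, clustering (PAM and DMM), correlation (CCLasso), ordination analysis (PCA and PCoA"), and for differences between genera. Proportions of key taxa (proteobacteria and firmicutes as examples) will also be compared, as will "numbers and presence of key species including lactobacilli, bifidobacteria and staphylococci".
- **Section 13.2.1, Microbiome (analysis plan):** ordination summarises community composition and identifies taxa linked to change over time. Then: "We will then use canonical ordination to quantify the impacts of the diet on the microbiome composition". Neither the Shannon index nor any between-arm comparison of diversity appears.

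Section 7 refers to a primary analysis that stays valid whatever share of intake is mother's own milk, but no section defines that analysis for the microbiome.

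**The concern.** A protocol may leave modelling detail to a statistical analysis plan, but it has to say what the primary endpoint is. Here a reader cannot tell whether the microbiome question is decided by Shannon diversity, by the proportion of Bifidobacteria, by another taxon, by a beta-diversity distance or by the canonical ordination. The measure behind the sample size is missing from the section headed as the analysis plan, and the method given there for the diet effect has no sample size of its own.

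Two things are at stake. First, in an open-label trial, a positive primary claim could rest on whichever measure happens to be significant. Second, the measures need not agree. Section 13.1.1 treats higher Shannon diversity as the more mature, lower-risk state, while dominance by a single taxon lowers it. The same data could look favourable on a taxon and unfavourable on diversity, with no rule for which counts.

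**Working it through.** **1. The four sections side by side**

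| Section | Measure | Time point | Between-arm comparison |
|---|---|---|---|
| 1 Summary | Diversity (index unnamed); taxa, by example | 34 weeks PMA, as basis for about 80 evaluable infants | Not stated |
| 8.1.1.1 | Assay only | None | Not stated |
| 13.1.1 | Diversity index (Shannon in context); beta diversity; genera; taxa; species | None | 0.5 SD in the index; others unsized |
| 13.2.1 | Community composition | Change over time | Canonical ordination |

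No row ranks the measures. Section 11.2.1 has stool collected daily to 34 weeks PMA and 11.4.1 mentions 188 samples, so analyses over time are feasible. One value per infant is suggested only by the 40 samples per group in 13.1.1.

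**2. The stated sample size**

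The only microbiome figure is 24 per group for over 95% power at 0.5 SD. Two-sided 5%, normal approximation: power = Φ(d·√(n/2) − 1.96).

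- n = 24: Φ(0.5 × 3.464 − 1.96) = Φ(−0.228) = 0.41 (0.40 by the t test).
- n = 40: Φ(0.5 × 4.472 − 1.96) = Φ(0.276) = 0.61 (0.60 by the t test).
- For 95% power: n = 2 × (1.960 + 1.645)² / 0.5² ≈ 104 per group.

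The figure does not reproduce. It would fit if 0.5 meant index units with an SD of about 0.47 or less (0.5/0.47 ≈ 1.06 SD), but the protocol gives no such SD. This is a separate defect. It matters here only because the fix relies on the same measure.

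**3. Chance of at least one false positive**

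Assumption: two-sided 5% per test. The protocol states that level only for body composition (13.1.2). For k independent tests the chance is 1 − 0.95^k. For correlated tests it is the probability that the largest |Z| among k equally correlated normal statistics exceeds 1.96.

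| Tests counted | r = 0 | r = 0.5 | r = 0.9 |
|---|---|---|---|
| k = 2: diversity and Bifidobacteria (summary) | 1 − 0.95² = 9.8% | 9.1% | 7.0% |
| k = 7: Shannon, UniFrac, proteobacteria, firmicutes, lactobacilli, bifidobacteria, staphylococci | 1 − 0.95⁷ = 30.2% | 23.0% | 11.4% |

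Adding canonical ordination as an eighth gives 1 − 0.95⁸ = 33.7% if independent.

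**4. Can taxa and diversity disagree?**

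Shannon = −Σ p·ln p, with illustrative communities of four taxa.

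- Even, 25% each: −4 × 0.25 × ln 0.25 = 1.39.
- One taxon at 70%, the others at 10% each: 0.250 + 3 × 0.230 = 0.94. Diversity falls as that taxon rises.
- Start at 85/5/5/5 (0.59) and let one minor taxon rise to 25%, scaling the others down to about 67/4/4: 0.87. Diversity rises.

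The direction therefore depends on whether the rising taxon becomes dominant.

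**The case against.** The strongest defence is that the sections are incomplete rather than opposed. Summary, objectives and 13.1.1 all speak of diversity and types of bacteria, and sequencing is simply the assay that produces both. Section 13.1.1 also says outright that alpha diversity will be analysed. A reader might infer that the powered contrast is never analysed, or that the definitions are incompatible. The text supports neither: the diversity comparison is promised under the sample-size heading and absent from the analysis section. Likewise, the summary does not state one stool per infant, and an analysis over time can sit beside a 34-week contrast.

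The second defence concerns size. No significance level is given for the microbiome, and five of the seven contrasts are not individually labelled primary. A reader might take 23% or 30% as the trial's error rate. It is not; it is what would follow if any of the seven were allowed to count. Only the 7-10% figure uses measures the summary labels primary.

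Third, Section 14 calls the trial exploratory, Section 4.4 calls it mechanistic, and a statistical analysis plan may rank the tests. This softens the consequence. It does not remove it: the protocol still labels primary endpoints and claims power and significance for them, and a later ranking would leave these four sections disagreeing.

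**Conclusion.** The point holds as an inconsistency in the definition of the primary endpoint. The protocol names a diversity index for sample size, an open list in the summary, an assay in the endpoint section and canonical ordination in the analysis section, with no statement of which decides. Assuming two-sided 5% per test, the chance of at least one false positive is 7-10% for the two measures named in the summary, and 11-30% across seven named contrasts as the common correlation goes from 0.9 to 0.

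Two tempting inferences go too far. A rise in a taxon such as Bifidobacteria does not necessarily lower Shannon diversity; it does so when that taxon comes to dominate, so conflict between the measures is possible but not certain. Nor can Shannon be called an adequately powered choice: at 0.5 SD the power is about 40% with 24 per group and about 60% with 40. It is the natural candidate because the protocol already uses it for sample size, not because the stated power is sound.

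**What to change.** In the summary, 8.1.1.1 and 13.2.1, name one deciding microbiome contrast in the same words. The most natural choice is the between-arm difference in Shannon diversity at 34 weeks PMA, one value per infant, at two-sided 5%. Add that comparison to 13.2.1. Label taxa, beta diversity, ordination and over-time analyses secondary or exploratory, with multiplicity control for the taxa.

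If the sponsor wants taxa to remain primary, name a single taxon and either split the alpha or use Holm across the two tests.

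The cost is wording in three sections; no extra infants or samples are needed. The downsides are real. Other taxon and ordination results can no longer be claimed as primary. Under an equal split (2.5% each), 40 per group has 80% power only for about 0.70 SD, against 0.63 SD for a single 5% test. The power statement in 13.1.1 must also be restated separately, because over 95% for 0.5 SD with 24 per group does not reproduce.

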4. BACKGROUND

4.1. Preterm birth

Prematurity is a major cause of mortality and serious long-term morbidity with a substantial burden on health and educational systems (~£3bn/year in the UK). Diseases such as necrotising enterocolitis (NEC, a serious inflammatory bowel disease) and sepsis are responsible for more deaths after the first postnatal week in every preterm infants than any other single pathology [1]. NEC and sepsis increase the risk of mortality and morbidity. Though widely believed to be related to feeding practices adequately powered and designed trials are lacking. NEC and sepsis are lower in infants receiving their own mother's breast milk, and cognitive outcomes are better, but the impact of pasteurized human donor milk is uncertain.[2]

301 302

303

304

305

306

307

308 309

310

311

312

313

314

315

316

317

318

Maternal milk is strongly promoted in all UK neonatal units and >90% infants now receive some mother's milk. However, the role of donor breast milk (DBM) remains uncertain because data on outcomes are inconsistent and many are smaller studies conducted several years ago when rates of mother's own milk provision were much lower. The most recent published randomized controlled trial[2] shows that the amount of mother's own breast milk remains strongly associated with improved health outcomes. However, there were no differences in the key clinical outcomes of NEC, sepsis or death between the two randomized groups exposed to donor milk compared to supplementation with cow's milk formula in the first 10 days of life. In another recently completed study there was no difference in the primary outcome of longer term neurodevelopment in those who received donor human milk compared to preterm formula used as supplements when there was a shortfall in provision of mother's own milk, but secondary analysis showed a difference in rates of NEC (all grades) [3]. These recent studies mean that there is still considerable uncertainty in the UK as to whether human donor milk should be used and current practices towards using formula or donor milk when there is a 'shortfall' in supply of mother's own milk differ between neonatal units[4]. National data show no clear differences between neonatal networks that do or do not use donor milk. Donor milk is considerably more expensive than formula milk.

319

4.2. Use of human milk fortifiers

One further issue arises in the use of human milk because the nutrient density both of mother's own and donor human milk, may be insufficient to meet the needs of very preterm infants. Many clinicians therefore fortify human milk with cow milk derived products. These human milk fortifiers increase short term weight gain but long-term evidence of benefit on functional outcomes is lacking. There are also no data examining more important longer-term outcomes. In addition, because fortifiers are of cow's milk origin, it is uncertain what other impacts they might have, for example on the pattern of gut bacteria. Emerging evidence show that the pattern of gut bacteria is associated with a range of health outcomes, but almost all studies to date are observational and subject to the inherent limitations of this type of design.

4.3. Human milk-based fortifiers

A recent new development is the production of commercial donor human milk derived fortifiers that can be used with mother's own or donor human milk enabling clinicians to meet nutrient intake recommendations [5] without exposure to cow's milk components. A recent trial conducted in the US [6] showed a decreased incidence of NEC in infants who received a human milk derived fortifier compared to cow's milk derived products, although not powered for this outcome. A further study supported these benefits in a trial using both donor human milk and human milk derived fortifier compared to preterm-formulated cow's milk formula in infants where maternal breast milk was not available [7]. Observational studies from the US support these data [8] and several US units now use these products. However, these products are not currently available in the UK.

4.4. Rationale for trial

Breast milk is associated with advantages for infants in both the short-term (lower sepsis rate) and longer-term (lower blood pressure, improved cognitive outcome) although the full range of functional benefits, and causal mechanisms are not well defined. Randomisation to breast feeding or formula is not acceptable as the former is recommended for all infants. However, mothers that deliver infants preterm frequently do not produce sufficient expressed breast milk to meet all their infants' milk requirements. In this situation, a cow's milk based infant formula or pasteurized donor human milk are options for use, with evidence for the better

choice remaining uncertain. Human milk (mothers' own or donor) is sometimes fortified with additional nutrients to prevent or treat faltering growth. Currently in the UK this requires the use of a milk 'fortifier' derived from cow's milk, hence very few very infants receive an exclusive diet of human milk. A new human milk fortifier has become available offering opportunity to compare the effect of an exclusive human milk diet, in comparison with a diet containing bovine products, on gut bacteria, metabolites, and body composition.

There are a number of reasons that preclude immediate UK adoption of human milk-based fortifier. Studies in the US have been small and inadequately powered to detect differences in functional health outcomes, and were conducted in hospitals with populations of babies with disease risks that may differ from UK settings. Health service costs applicable to the UK have not been determined so cost-effectiveness is uncertain, and causal mechanisms have yet to be explored.

The proposed trial is a mechanistic study to explore the impact of dietary strategies on gut bacteria, metabolism and body composition. The trial is neither designed nor powered to detect differences in clinical outcomes. However, data on clinical outcomes might contribute to future meta-analyses. Protocol design, study conduct, analyses, and decision to publish are the responsibility of the investigator team completely independent of the funder (Prolacta Bioscience). The Sponsor (Newcastle Hospitals NHS Foundation Trust) will play no role in data analyses but will provide governance oversight for the study as NHS sponsor.

